A VAMC Research and Development (R&D) and Medical University of South Carolina (MUSC) Institutional Review Board (IRB) approved pilot project was completed in Veterans with depressive/anxiety disorders and related comorbidities to assess feasibility and efficacy of TBT ([name], 2014). The trial involved an initial evaluation, revision/refinement of the protocol, and then a second evaluation of the revised version. In the first trial, 15 Veterans were recruited to complete the treatment. All participants were diagnosed with multiple comorbid depressive/anxiety disorders, and reported severe, pre-treatment symptoms of anxiety and depression. Twelve of the fifteen participants finished TBT (80.0%). Treatment completers attended an average of twelve 50-minute sessions. As presented in Table 2, participants demonstrated significant improvements in symptoms across all disorders and comorbidities.

Table 2: Efficacy of Initial TBT Protocol in Veterans with Depressive/Anxiety Disorders

Scale	Pre M (SD)	Post M (SD)	t (p)	d
IIRS-Impairment	66.0 (14.9)	41.2 (19.8)	6.4 (< .001)	1.42
PTSD Checklist	56.1 (13.1)	37.0 (14.0)	5.6 (< .01)	1.41
DASS-Depression	13.1 (5.4)	5.2 (5.2)	5.3 (< .001)	1.51
DASS-Anxiety	12.6 (5.4)	5.9 (4.6)	5.5 (< .001)	1.35
DASS-Stress	13.2 (5.4)	7.9 (4.8)	3.6 (< .01)	1.04

Results from the initial pilot project were used to inform minor revisions of the TBT protocol. The revisions involved further focusing the TBT protocol on a transdiagnostic behavioral approach (i.e., exposure therapy), and relegating other CBT techniques to secondary/optional modules that could be provided later in treatment, if needed to improve exposure success ([name], 2014). In the second trial, 29 Veterans were recruited and all participants were diagnosed with multiple comorbid depressive/anxiety disorders and reported severe pre-treatment symptoms and impairment. The 21 participants completed treatment (72.4%). As presented in Table 3, participants demonstrated significant improvements in symptoms across all disorders and comorbidities.

Table 3: Efficacy of Revised TBT Protocol in Veterans with Depressive/Anxiety Disorders

Scale	Pre M (SD)	Post M (SD)	F (p)	d
IIRS-Impairment	64.2 (13.7)	39.4 (17.0)	45.8 (<.001)	1.61
PTSD Checklist	57.8 (14.8)	33.7 (10.9)	47.1 (< .001)	1.42
DASS-Depression	12.4 (6.1)	5.1 (4.4)	45.9 (< .001)	1.37
DASS-Anxiety	11.1 (5.3)	5.2 (3.5)	42.1 (< .001)	1.31
DASS-Stress	13.8 (5.0)	7.3 (3.8)	38.0 (< .001)	1.46

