The MITT analysis set will comprise all randomized participants. Missing data in the full analysis set will occur if participants discontinue treatment prior to the end of the study or do not complete an outcome measure. In general, participants will remain in the study unless consent is withdrawn or if there are concerns regarding participant safety. However, participants will be required to complete the full course of treatment (12 sessions) within a maximum of 18 weeks, in order to maintain the integrity of the treatments (Barlow et al., 2017). If participants fail to do so within 18 weeks, treatment will be discontinued and follow-up assessments will be completed. Missing data for the MITT analysis set will be accounted for using full information maximum likelihood (ML), which is superior to most alternative missing data approaches even when data is missing completely at random (MCAR) or missing at random (MAR; Schafer & Graham, 2002; Enders, 2010). Although the use of ML will result in the least biased parameters, regardless of data missingness, several approaches will be undertaken to better understand the exact mechanisms for missing data. Little's (1988) MCAR test will be applied to all final models to determine whether data can be considered MCAR. Further, the results of analyses using study completers and protocol adherers (completer and per-protocol analyses) will be compared with results using the MITT analysis set to test sensitivity of study conclusions to study discontinuations and protocol non-adherence. Baseline differences also will be explored between treatment completers and those that discontinue. If baseline differences are detected, these covariates will then be included in the final model as auxiliary variables to improve the plausibility of assuming data is MAR (Collins et al., 2001; Enders, 2010; Graham, 2003;). Finally, discontinuation proportion will be used as one of the outcome measures of intervention feasibility.

Efficacy Measures Analyses (Primary Aim)

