17. *SAFE-TBT*. The SAFE-TBI was designed to identify the level of evidence for exposure to mild TBI (McAllister et al., 2016). The SAFE-TBI includes a definition of mild TBI as well as three multi-part screening questions, regarding: 1) exposed to, screened for, or put on restricted duty due to any head or brain injury from six examples (e.g., blast or explosion); 2) associated symptoms that occurred immediately after the head or brain injury (e.g., duration of loss of consciousness, feeling dazed or confused, amnesia); and 3) memory loss of events just before or after the injury. The SAFE-TBI has demonstrated moderate levels of agreement for inter-rater and test-retest reliabilities (McAllister et al., 2016). In addition, the SAFE-TBI demonstrated reasonable convergent validity with more extensive measures of TBI in a VA sample.
18. *Veterans Short-Form Health Survey (V/SF-36)*. The V/SF-36 is a 36-item measure designed to assess functional health, well being, and quality of life in Veterans, and can be scored to produce two primary subscales for physical health and mental health (Kazis, 2000). The V/SF-36 was adapted from the original SF-36, which has received extensive support in the literature (Ware & Sherbourne, 1992).

Participants will be asked to complete the assessment materials four times throughout the duration of treatment: pre-treatment, mid-treatment (session 6), post-treatment and six-month follow-up. Participants also will complete select measures bi-weekly to monitor treatment progress.

Potential Risks

There is a potential psychological risk of emotional discomfort during the assessment and treatment procedures. Although this reaction is not uncommon in exposure-based treatments of anxiety and depression and typically is brief in its duration, there are several provisions to reduce and/or avoid it in the proposed study. First, the proposed treatments are designed specifically to target the reduction of emotional distress, anxiety, and

avoidance. Second, if a participant expresses a desire to discontinue treatment due to distress and/or a study clinician determines that participation is counter-indicated, all research and treatment procedures will be terminated.

There is a risk of a loss of confidentiality of personal information as a result of participation in this study. There is a risk of being randomly assigned to a treatment condition that is less effective than the other.

ADEQUACY OF PROTECTION AGAINST RISKS

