Recruitment and Informed Consent

All eligible and willing VAMC patients will be required to meet with project staff to review the purpose of the study and review the consent documentation. VAMC patients will be given ample time to discuss the study and ask questions regarding the procedures. Upon thorough review of all documentation, VAMC patients will sign the informed consent document before any study procedures are initiated.

Protection against Risk

1. Participants will be made aware of the potential risks and benefits associated with participation and their right to withdraw from the study at any point without any negative impact on their care within the VAMC. Any participants expressing interest in withdrawing from the study will be referred for treatment within the VAMC.
2. Participants who appear unable to tolerate the assessment process will be offered a referral to the VAMC and terminated from the study procedures.
3. As members of the mental health service at the VAMC, the Principal Investigator and Co-Investigator will maintain active collaborations and communications with other VAMC providers to ensure appropriate continuity of care and safeguard against any adverse events.

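### The protocol conflicts with itself on whether outcomes are still collected after a participant stops treatment because of distress; read literally, one passage discards the primary outcome for a reason plausibly linked to it.

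*Combined protocol and SAP*

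**What the plan says.** Four places bear on what happens to outcome collection when treatment stops.

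- **Protection of Human Subjects, Potential Risks.** The trigger is "if a participant expresses a desire to discontinue treatment due to distress and/or a study clinician determines that participation is counter-indicated". The consequence is that "all research and treatment procedures will be terminated". The trigger has two limbs: the participant's own wish, and a clinician's judgement.
- **Missing Data.** The general rule is "In general, participants will remain in the study unless consent is withdrawn or if there are concerns regarding participant safety". For participants who do not finish 12 sessions in time: "If participants fail to do so within 18 weeks, treatment will be discontinued and follow-up assessments will be completed".
- **Assessment section (quality of life, symptoms and satisfaction).** Follow-up assessments are promised for all participants, with no exception for those who stopped treatment.
- **Protection against Risk, item 2.** A separate rule covers the assessments themselves: "Participants who appear unable to tolerate the assessment process will be offered a referral to the VAMC and terminated from the study procedures".

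On analysis, the primary time point is the end of active treatment and the analysis set is everyone randomized. Missing data are handled by full information maximum likelihood. The checks are Little's MCAR test, auxiliary variables chosen from baseline differences, and comparisons with completer and per-protocol analyses. No analysis allows for data missing not at random.

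**The concern.** A participant who asks to stop therapy because of distress has not thereby withdrawn consent to research. Nor is a wish to stop therapy, without more, the safety concern that the Missing Data section has in mind. For that person one section says to end assessments and two others point to continuing them.

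If the Potential Risks wording is followed, the post-treatment and 6-month outcomes are never collected. The participant still counts in the analysis set, but the primary outcome has to be inferred from what came before. Stopping because of distress is plausibly related to how the participant is doing, which is the setting in which missing at random may fail. At stake is the between-arm estimate on which the non-inferiority conclusion rests. Outcomes that were not collected cannot be recovered afterwards.

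**Working it through.** **1. Do the passages conflict?** Take three kinds of stop.

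| Reason for stopping treatment | Potential Risks | Missing Data and assessment sections |
|---|---|---|
| 18-week limit passed | not addressed | assessments completed |
| Clinician judges participation counter-indicated | research ends | can fit the safety exception |
| Participant wants to stop because of distress, consent not withdrawn | research ends | neither exception clearly applies; follow-up is for all |

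Only the third row is a conflict. The Missing Data section also says that missing data will occur when participants discontinue treatment, so it expects some discontinuers to have no outcome. It does not settle the matter either way.

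**2. Do the planned checks cover the loss?** Maximum likelihood relies on missing at random. Completer and per-protocol analyses leave out largely the same people. Little's test examines missing completely at random and cannot separate missing at random from not at random. The auxiliary variables are chosen on baseline differences only.

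**3. How large could the bias be?** The plan gives no figure to reproduce here: no distress-stop rates, and no attrition rate behind the total of 306. The inputs are:

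- 153 per arm = 306/2, from the planned total and 1:1 allocation. (The Randomization Procedures give 108 per arm; that is a separate matter.)
- One-sided alpha .006 and margin 0.5 SD, from the sample size section. (The efficacy analysis section states a margin of 0, also a separate matter.)
- Loss rates p and deviation k, where k is how many SD worse lost participants are than the model predicts. Both are assumptions.

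With a common k, bias in favour of TBT = (p_TBT − p_DST) × k. In general it is the arm difference in p × k.

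- Equal loss and equal k: bias 0.
- 10% v 5%, k = 0.5: 0.05 × 0.5 = 0.025 SD.
- 10% v 5%, k = 1.0: 0.05 × 1.0 = 0.05 SD.
- 5% v 10%, k = 0.5 to 1.0: −0.025 to −0.05 SD.

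**4. What does that do to the error rate?** SE = √(2/153) = 0.1143 and z(.994) = 2.512. When TBT is truly worse by exactly the margin, P(non-inferiority claimed) = Φ(bias/SE − 2.512).

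- Bias 0: Φ(−2.512) = 0.6%.
- Bias 0.025: Φ(0.219 − 2.512) = Φ(−2.293) = 1.1%.
- Bias 0.05: Φ(0.437 − 2.512) = Φ(−2.075) = 1.9%.
- Bias −0.025: Φ(−2.731) = 0.3%.
- Bias −0.05: Φ(−2.949) = 0.2%.

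The formula does not contain the margin, because it is evaluated at the margin. The conflict between 0.5 and 0 therefore leaves these rates unchanged. Allowing for the assumed loss in the SE (137.7 and 145.35 participants; SE = √(1/137.7 + 1/145.35) = 0.1189) changes 1.1% and 1.9% to 1.1% and 1.8%.

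**5. Does the mechanism matter?** A small simulation used 153 per arm and a likelihood-type estimate based on baseline and mid-treatment scores, with loss of 15% in TBT and 5% in DST. Bias was about 0 when stopping depended on the observed mid-treatment score. It was about 0.10 SD towards non-inferiority when stopping depended on the unobserved outcome. With the rates swapped, the second figure had the same size and the opposite sign.

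**The case against.** Four points on the other side have force.

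- **The arm and the direction.** A reader might infer that the loss will be greater under TBT, because the preliminary studies describe it as refocused on exposure and Potential Risks says distress is not uncommon in exposure-based treatment. The documents do not support that step. The remark is general, and the exposure content of the DSTs and stop rates by arm are not given. The DSTs were chosen for their similar cognitive-behavioral techniques, and the secondary hypothesis expects TBT to do better on discontinuation. A pull towards non-inferiority is therefore conditional.
- **Who is lost.** A reader might also infer that those doing worst are lost. The trigger is distress or clinician judgement, not a score. Worsening scores fall under a separate provision in the Data and Safety Monitoring Plan, which offers alternative treatment and does not say that assessments end.
- **Scores before the stop.** PHQ-9, PDSS and PCL-5, three of the four primary outcomes, are taken every other session. If they enter the model, they could remove much of the bias. The efficacy section does not say that they do. STICSA is not in that list, although the monitoring plan names it among biweekly measures.
- **Participant protection.** The risk being addressed includes discomfort during assessment, and a clinician's counter-indication can fit the safety exception. Both stand, and they limit the fix to participant-initiated treatment stops.

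None of this removes the conflict for a participant who only wants to stop therapy. The consent pages are not available, so what they say about follow-up after stopping treatment cannot be checked.

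**Conclusion.** The point holds as a contradiction with an avoidable cost. One passage ends outcome collection after a participant-initiated distress stop, while two others point to continuing it. Followed literally, it creates missing primary outcomes that the planned analyses cannot be relied on to handle.

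The size and direction of any bias are unknown. It is zero if loss rate times deviation is the same in both arms, and it favours TBT only if that product is larger under TBT. The illustrative 0.025 to 0.05 SD, with false non-inferiority of about 1.1% to 1.9% instead of 0.6%, rests on assumed loss of 10% v 5%, an assumed deviation of 0.5 to 1.0 SD and 153 per arm. With the loss rates swapped, the error is conservative (0.2% to 0.3%). Confidence is medium: the textual conflict is plain, but its numerical effect is not established.

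**What to change.** Reconcile Potential Risks, Missing Data and the assessment section by separating stopping treatment from withdrawing from research. Where a participant chooses to stop treatment and has not withdrawn research consent, continue to offer the post-treatment and 6-month assessments already scheduled, which the participant may decline. Leave unchanged the clinician's counter-indication decision and the rule for participants who cannot tolerate assessment. Nothing here alters when treatment stops.

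The feasibility analysis already tabulates reasons for discontinuation, so distress stops can be counted by arm from that record. State in the efficacy section whether the every-other-session scores enter the primary model.

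This is a cheap improvement. It costs protocol wording, consent wording if needed, and a few more contacts with people who have stopped therapy.

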Participants will have the option of signing the informed consent via Docusign. The informed consent and HIPAA documents will be uploaded via the VA's Docusign Research Use Request Sharepoint portal. Study staff will explain, in detail, each aspect of the informed consent form and HIPAA authorization before instructing the participant to electronically sign the documents. Copies of the completed forms will be stored electronically on the VA secured research drive behind the VA's firewall. Printed copies will be kept in locked cabinets inside locked offices in preparation for VA audits. Access to both electronic and printed copies will be restricted to authorized study personnel on the IRB personnel list and Delegation of Authority log.

Eligibility Criteria

Inclusion criteria: 1) participants must be clearly competent to provide informed consent for research participation, 2) participants must meet DSM-5 criteria for either MDD, PTSD, or PD/AG, and 3) participants must be 18 - 80 years of age. **Exclusion criteria involve:** 1) recent history (≤ 2 months) of psychiatric hospitalization or a suicide attempt and/or suicidal ideation with acute intent as documented in their medical record or reported during clinical interview, 2) acute, severe illness or medical condition that likely will require hospitalization and/or otherwise interfere with study procedures as documented in their medical record (e.g., active chemotherapy/radiation treatment for cancer), 3) recent start of new psychiatric medication (≤ 4 weeks), or 4) diagnosis of traumatic brain injury (TBI) in their medical record and/or endorsement of screener questionnaire (McAllister et al., 2016). Additional comorbid psychiatric diagnoses that were not listed as exclusion criteria are permitted as long as they are considered secondary to the principal diagnosis of MDD, PTSD, or PD/AG as determined by the diagnostic interview. Of note, if participants request changes to their psychiatric medications at any time during the treatment, a medication consult will be completed with a prescriber in VA Mental Health. Any changes in medications and/or initiation of non-study psychotherapy will be recorded for inclusion in the analyses as a possible covariate. Ineligible Veterans will be referred for non-study-related treatments within mental health at the RHJ VAMC.

Procedures

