For all study outcomes (ADIS-5, IIRS, PCL-5, PDSS, PHQ-9, and STICSA), Veterans will be randomly assigned (1:1) to the TBT and specific DST conditions. The power analysis was calculated to be powered at 80% with a Bonferroni-corrected 1-tailed $\alpha = .006$ (.025/4 primary outcomes) to detect non-inferiority for TBT in comparison to the aggregated DST effect. Meta-analyses for CBT for MDD, CPT for PTSD, and CBT for PD/AG reveal large treatment effects (CBT for MDD bias-adjusted $g = .53$; Cuijpers et al., 2013; CPT for PTSD in military personnel $g = 1.33$; CBT for PD $g = 0.35$; Hofmann & Smits, 2008). Thus, the average effect size for DSTs was expected to range from small-to-medium to large. A power analysis was conducted using procedures recommended by Chow, Shao, and Wang (2017), Flight and Julious (2014), and Julious (2004) as well as recommendations by the United States Food and Drug Administration and the European Medical Association (Food and Drug Administration, 2017). An important topic in non-inferiority designs is selection of the “appropriate” prespecified non-inferiority limit. Current best practice involves selecting a non-inferiority margin that is not greater than the smallest effect size expected for the DSTs in comparison to a control condition. As a tradeoff between sample size needs and feasibility of recruitment, we conducted power analysis setting the non-inferiority margin to 0.5, indicating that we would consider TBT non-inferior to the DSTs if TBT were to perform less than half a standard deviation worse than the DSTs. We set the expected group different to 0.3 given our pilot data demonstrating that TBT outperforms DSTs by this margin across primary outcome variables. Using procedures recommended by Chow, Shao, and Wang (2017) for non-inferiority designs, which utilize the pre-specified non-inferiority margin (here prespecified as $\Delta d = 0.5$) and the estimated effect in the active comparison treatment ($d = 0.3$), we determined that 144 participants (72 per cell) would be needed. However, this does not account for potential attrition or for potential design effect issues involving therapist effects or for potential missing data related to telehealth delivery of services. To account for possible attrition and missing data as well as the potential influence of design effects, we increased the sample size to 306 participants based on the data available to date. Based on pilot data, we expect to find large within-person effects ($d \geq .80$) for TBT, indicating 4/5ths of a SD reduction in each of the primary outcome measures. This sample size would leave us powered to detect small-to-medium within-person effect sizes.

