The continuous measures included measures of disorder severity scales (ADIS-5), disorder-specific symptomatology (PCL-5, PDSS, PHQ-9, and STICSA), general related symptomatology (STISCA), and quality of life and impairment (IIRS). Of these variables, the PCL-5, PDSS, PHQ-9, and STICSA are the primary outcomes of interest. All other analyses will be conducted in an exploratory fashion to inform future studies and compare findings to previous studies ([name], 2014; [name] et al., 2017; 2019). Parameter estimates to calculate the effect size difference will be arrived at using three-level (measurement occasions nested within participants nested within assigned treatment condition) generalized mixed-effects regression models (MRM). MRM is a method of repeated measures analyses that allows for modeling of continuous and categorical independent and dependent variables and for appropriate modeling of covariance structures when observations are correlated across time and/or across condition. This analytic approach fully captures variability in outcomes across multiple follow-up assessments and accounts for any potential effect of the group to which a participant is assigned and is thus preferred over methods that collapse data over time. We will calculate between-group treatment differences as Cohen's d, based on the effect of treatment condition on the intercept parameter when the model is centered on post-intervention and on the effect of treatment condition on the intercept parameter when the model is centered on month 6. We prespecified the non-inferiority margin (d) to be 0 (indicating we expected TBT to be at least equivalent to the aggregate DST effect) and the one-sided CI for our four primary analyses at $\alpha = .006$. In the primary analyses of outcome variables, we will covary for the baseline value of the variable of interest. We also will include the linear effect of time as well as a time by condition interaction effect to determine whether treatment differences (or lack thereof) were stable from post-intervention through the follow-up. Additional covariates (e.g. age, number of psychiatric comorbidities, race, sex, combat theatre, number of treatment sessions, specific DST received) will be added to the model to adjust for putative confounding variables. Effect size CIs that do not contain 0 provide evidence in support of noninferiority for TBT. The primary outcome time point is at the end of the active treatment phase and the secondary time point is at the end of the naturalistic 6-month follow-up period. Further, within-subject effect sizes from baseline to post-intervention and to 6-month follow-up also will be calculated within the TBT condition to quantify TBT-specific reductions in symptoms. These analyses will be probed to examine potential therapist effects. First, design effects will be calculated for the primary outcome variables. Design effects > 2 are often used as a heuristic to judge when these effects can be problematic.

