4. All assessment and treatment providers will be trained and supervised by the Principal Investigator, Co-Investigator, or one of the staff psychologists involved in the study, each of which is a licensed psychologist. At intake, participants identified by clinical interview with suicidal ideation and acute intent will be excluded from the study and immediately offered emergency psychiatric care at the VAMC. All participants will be completing the PHQ-9 biweekly during the active treatment, in addition to completing those measures and several others at the mid-treatment, post-treatment, and 6-month follow-up time points. During each assessment, the PHQ-9 item 9 will be inspected by the treating therapist/assessor for the presence of suicide ideation (≥ 1 on item 9). If identified, the Columbia Suicide Severity Rating Scale (C-SSRS) will be completed in CPRS. If the C-SSRS is positive, the staff will initiate a warm handoff to a provider in PCMH or Mental Health with support of the project team ([name] is a supervisor in Mental Health) to complete a comprehensive suicide risk assessment. If hospitalization is needed, the PCMH/MHC staff will initiate that process. Upon completion of the warm handoff and comprehensive suicide risk assessment, the provider, research staff, and clinical supervisor ([name]) will discuss ongoing plan. If suicidal ideation is present but not intent, the participant will be retained in the study and reassessed for suicide risk by the investigators in one week. In cases of acute suicidal intent, state law requires immediate hospitalization and these guidelines will be followed.
5. Treatment progress will be assessed throughout the active treatment phase through participant interactions with the therapist as well as completion of self-report measures. Participants who do not respond to treatment or do not complete 12 sessions within a maximum of 18 weeks will be offered mental health treatment with an appropriate VAMC provider.
6. All adverse events associated will be reported to CSR&D program officers and relevant IRBs and data monitoring boards.
7. All participants will be informed if significant information is discovered about the treatment or if other more effective treatment interventions are discovered.

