The proposed investigation includes a clinical trial that involves the comparison of a newer evidence-based psychotherapy, TBT, with established evidence-based psychotherapies, CPT, CBT for Depression, and CBT for PD/AG. Both treatment conditions involve active treatments have been shown to be effective in addressing symptoms in the selected disorders/population. Several steps were included in the proposed clinical trial for subject safety and minimizing risks of the research.

1. Treatment progress will be assessed throughout the active treatment phase (baseline to final session of psychotherapy) through participant interactions with the project therapist, self-monitoring and other between session exercises, biweekly self-report measures of various psychiatric symptoms (e.g., DASS, IIRS, & STICSA), and mid-treatment and immediate post-treatment assessments. Participants who demonstrate worsening of symptoms at any point in treatment (i.e., 25% increase in symptom severity for two consecutive assessment points) or do not demonstrated any symptoms improvement at the midway point in treatment (session 8) will be offered alternative mental health treatments with appropriate VAMC providers. Similarly, alternative mental health treatments with appropriate VAMC providers will be offered at the 6-month follow-up assessment point to all participants, regardless of symptomatology.
2. During the active treatment phase, participants will be monitoring weekly during their psychotherapy appointments. Monitoring will involve interactions with the project therapist, self-monitoring and other between session exercises, and biweekly self-report measures of various psychiatric symptoms (e.g., DASS, IIRS, & STICSA).
3. Monitoring will be completed by the project therapist and reviewed by the Principal Investigator during weekly supervision meetings.
4. The study will be end at the completion of the 6-month follow-up assessment. Alternative mental health treatments with appropriate VAMC providers will be offered at the completion of the 6-month follow-up assessment point to all participants, regardless of symptomatology.

F. REFERENCES/LITERATURE CITATIONS

Barlow, D. H., Allen, L. B., & Choate, M. L. (2004). Toward a unified treatment for emotional disorders. *Behavior Therapy*, 35, 205-230.

[name], D. F. (2014). Development and initial evaluation of Transdiagnostic Behavior Therapy (TBT) for veterans with affective disorders. *Psychiatry Research*, 220, 275-282.

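### Outside treatment offered because a participant is doing badly is proposed as a covariate; this biases the arm comparison and can hide a true TBT deficit, and no rule covers scores after a switch

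*Combined protocol and SAP*

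**What the plan says.** Two safety sections offer care outside the study, and both apply to either arm.

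- **Data and Safety Monitoring Plan, item 1.** The offer goes to participants whose severity rises by a quarter at two assessments in a row, at any point in treatment, and to those with no improvement by the midpoint: "session 8) will be offered alternative mental health treatments with appropriate VAMC providers".
- **Protection against Risk, item 5.** "Participants who do not respond to treatment or do not complete 12 sessions within a maximum of 18 weeks will be offered mental health treatment".

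The Eligibility Criteria section says how such care enters the analysis, and Risks to the Subjects repeats it: "Any changes in medications and/or initiation of non-study psychotherapy will be recorded for inclusion in the analyses as a possible covariate".

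Under Missing Data, the MITT set is everyone randomised, and participants stopped at 18 weeks are still assessed. Completer and per-protocol analyses are planned for comparison with MITT. Per-protocol is not defined there, and nothing says whether starting outside care is a departure from protocol.

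Under Efficacy Measures Analyses, the primary time point is the end of active treatment, and "the secondary time point is at the end of the naturalistic 6-month follow-up period". The covariate list there is open-ended. It does not name outside therapy, but it does include another post-randomisation variable, the number of sessions. No section says whether scores recorded after outside treatment begins are used, set to missing or modelled.

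**The concern.** The offer is triggered by a poor course on the assigned treatment, so outside treatment lies downstream of randomisation. A model that includes it compares TBT and DST participants of like switching status. If TBT is worse, more of its participants switch, and the covariate absorbs part of the deficit that the trial exists to detect.

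There is a second, conditional route. If TBT is worse, more TBT participants take up outside care and they benefit from it, their later scores improve the TBT mean. In a non-inferiority trial that movement favours the new treatment. The 6-month contrast is the more exposed: every one of these offers can precede it, and it is used to judge whether any difference is stable. The post-treatment visit is exposed only through offers made during treatment.

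**Working it through.** **Inputs from the plan.** Sample Size Determination is "powered at 80% with a Bonferroni-corrected 1-tailed $\alpha = .006$ (.025/4 primary outcomes"), and describes "setting the non-inferiority margin to 0.5". Efficacy Measures Analyses says "We prespecified the non-inferiority margin (d) to be 0". Total enrolment is 306, so 153 per arm; Randomization Procedures gives 108 per arm. No uptake rate is given.

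**The plan's own figure.** It states 72 per arm (144 in total) and also "We set the expected group different to 0.3", with TBT the better. With SD 1, n per arm = 2 × (2.512 + 0.842)² / (0.5 + 0.3)² = 35.2, so 36 per arm or 72 in total. The stated 144 is twice that. Nothing below depends on it.

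**Assumptions for illustration.** True change is 0.8 SD on DST and 0.3 SD on TBT, a deficit equal to the 0.5 margin. The SD of change is 1. No improvement means change below 0. Of those participants, 50–100% take the offer and gain 0.5–1.0 SD by month 6, equally in both arms.

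**Route 1: scores used, no adjustment.**
- No improvement: Φ(−0.3) = 0.382 on TBT, Φ(−0.8) = 0.212 on DST; excess 0.170.
- Dilution = 0.170 × uptake × gain = 0.043 to 0.170 SD, so the observed deficit is 0.46 to 0.33 SD.
- SE = √(2/153) = 0.114.
- False non-inferiority = P(Z > 2.512 − dilution/0.114): 0.6% with no dilution, 1.6% at 0.043, 15.3% at 0.170.

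**Route 2: switching added as a covariate.** The adjusted deficit is the unadjusted deficit plus b × the excess in switching, where b is the pooled within-arm switcher-minus-non-switcher difference.

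| Uptake | Gain | Unadjusted | b | Excess | Adjusted |
|---|---|---|---|---|---|
| 50% | 0.5 | 0.457 | −0.846 | 0.085 | 0.385 |
| 50% | 1.0 | 0.415 | −0.346 | 0.085 | 0.385 |
| 100% | 0.5 | 0.415 | −1.165 | 0.170 | 0.217 |
| 100% | 1.0 | 0.330 | −0.665 | 0.170 | 0.217 |

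Adjustment leaves 0.22–0.39 SD of a true 0.5 SD deficit, less in every row than no adjustment.

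**Completer-type analysis.** If everyone without improvement is excluded, mean change among the rest is 0.92 on TBT and 1.17 on DST. The deficit appears as 0.25 SD.

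**Sensitivity of Route 1 (margin 0.5, true deficit 0.5).**

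| Setting | False non-inferiority |
|---|---|
| 108 evaluable per arm | 1.4–10.3% |
| 72 evaluable per arm | 1.2–6.8% |
| TBT 0.8, DST 1.3; 153 per arm | 1.2–6.6% |
| TBT 1.3, DST 1.8; 153 per arm | 0.9–2.4% |
| 30% TBT, 20% DST switch, gain 0.5; 153 per arm | 1.9% |
| 20% in both arms, gain 0.5; 153 per arm | 0.6% |
| 20% TBT, 30% DST switch, gain 0.5; 153 per arm | 0.16% |

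**Margin 0.** A deficit diluted towards zero cannot exceed the nominal 0.6%. A true 0.1 SD deficit diluted by 30% gives 0.09% at 153 per arm.

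**The case against.** The case against is substantial, and it rules out several stronger readings that a reader might infer.

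- **That the covariate is the plan's only safeguard.** Completer and per-protocol analyses are also planned. They do not repair the problem: they too select on post-randomisation behaviour, and they leave the status of outside treatment open.
- **That a TBT deficit will be diluted.** The offers go to both arms and may be declined. Dilution needs more, or more effective, switching on TBT. The sample size section expects TBT to do better, in which case DST participants might switch more and the test would be conservative.
- **That the primary visit is as exposed as month 6.** After session 8 of 12 weekly sessions about 4 weeks remain, or about 10 if treatment runs to week 18. Participants stopped at 18 weeks may be assessed before any offer takes effect.
- **That TBT failures cross over to the comparator therapies.** The site has CBT programs and a PTSD Clinical Team (Facilities Available), so this is plausible, but the documents do not list what is offered.
- **That 15% is a forecast.** It needs full uptake, a 1.0 SD gain, no attrition and a TBT change of 0.3 SD, whereas the plan expects at least 0.80 SD within person. The calculation also applies end-of-treatment change on one measure to a session-8 rule. Some switchers will have no later scores, since Potential Risks ends all research procedures when a participant stops for distress or on clinician judgement.

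Counting all outcomes regardless of later care is a legitimate choice, and calling the follow-up naturalistic is compatible with it. What stands is that the plan does not state that choice, and that the covariate it does propose works against it.

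**Conclusion.** The point holds in this limited form. Outside psychotherapy and medication change should not be covariates in the efficacy models: under the stated assumptions adjustment reduces a true 0.5 SD deficit to about 0.22–0.39 SD, a larger distortion than leaving scores unadjusted. Unadjusted dilution is conditional on more effective switching on TBT and falls mainly on month 6. The rise from 0.6% to about 1.6–15% is an illustration that rests on the 0.5 margin, 153 evaluable per arm and assumed uptake and gain. It disappears with equal switching and equal gain, or under a margin of 0, although under either margin the estimated difference can still be distorted. The documents do not support a claim that the trial's conclusion is already compromised. They support a cheap correction to the analysis plan.

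**What to change.** Leave the clinical offers unchanged.

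1. In Eligibility Criteria and Risks to the Subjects, delete outside psychotherapy and medication change as candidate covariates for the efficacy models. State that they will not be added under the open list in Efficacy Measures Analyses.
2. Keep the MITT analysis of all observed scores as primary, and say explicitly that it includes scores after outside treatment starts.
3. Add one prespecified sensitivity analysis at post-treatment and month 6 in which scores after outside treatment starts are not credited to the assigned arm. For example, set them to missing and impute from same-arm participants with a similar course before the switch. Report it beside the primary result. Requiring both analyses to meet the margin would change the decision rule and cost power, and is not needed.
4. Record the start date and type of outside treatment, and tabulate uptake by arm.
5. Say whether starting outside treatment is a per-protocol departure.

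Separately, two conflicts must be reconciled: the midpoint, given as session 6 (Sources of Materials) and session 8 (Data and Safety Monitoring Plan); and the margin, given as 0.5 (Sample Size Determination) and 0 (Efficacy Measures Analyses).

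The cost is plan wording, two form fields, one table and one extra analysis. That analysis will have a somewhat wider interval and rests on untestable assumptions about the course without the switch.
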